3.2 Analysis population(s)

The **full study population** will include all patients that satisfy the study inclusion criteria. This population set will be used for all secondary [REDACTED] efficacy analyses and for safety analyses.

The **efficacy population** is a subset of the full study population, which will be used for the analysis of the primary endpoint and includes patients who meet the following criteria:

- Patient had at least one target lesion
- Patient had an imaging scan performed on the index date (or up to 24 weeks prior to the index date) for at least one target lesion

3.3 Key post index date time points for reporting endpoint over time.

Considering the retrospective nature of the study, patients might have data available at different time-points. In order to maximize the use of data abstracted, key time points and associated time windows are identified for reporting purpose. For each of these time-points or intervals all patients with data available will be used. The total number of patients in a time interval will be equal to the number of patients with at least one valid assessment in that specific time window. The number of patients (N) in each interval will be summarized in the disposition table and used throughout the report. Only the time points with data available for at least 10% of the patients will be displayed in the corresponding output.

Key study time points are summarized in [Table 3-1](#).

Table 3-1 Time windows for post-index date key-time point

Key time-points	Allowed windows
4 weeks	Up to 10 weeks
12 weeks	[10 to 20 weeks[
24 weeks*	[20 to 32 weeks[
36 weeks	[32 to 40 weeks[
52 weeks	[40 to 58 weeks[
End of study	4 weeks prior to and up to min(study treatment discontinuation + 30 days, cut-off date)

* 24 weeks or 6 months (+/- 4 weeks).

After week 52 intervals of approximately 11 weeks (e.g. 63 weeks, 74 weeks, etc.) with a time window of +/- 5 weeks will be used until the "end of study".

Week 24 windows (+/- 4 weeks) is intended to include assessments performed 24 weeks or 6 months after index date, where 6 months is approximated to week 27.

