The last interval, referred to as "end of study" in [Table 3-1](#), will include data available within the last 4 weeks prior to study treatment discontinuation plus 30 days or cut-off date, whichever comes first. When a patient discontinues data will be reported in the "end of study" time window as well as the one corresponding to the assessment (e.g., a patient discontinued treatment at week 58 data will be reported in the key point 52 weeks interval and in the "end of study").

In instances where more than one measure is reported in the time window associated with a key time-point (e.g., at 12 weeks), the measurement taken closest to the key-time point will be considered in the analysis. If two measures were taken on dates that are equidistant from the key time-point (e.g., 12 weeks - 5 days and 12 weeks + 5 days following the index date), the measure associated with a more severe condition (e.g., larger non-target lesion volume, higher pain severity score, lower functional assessment score) will be considered.

In instances where both a non-missing value and a missing or unknown value are reported in the time window associated with a key time-point, only the non-missing value will be considered in the analysis.

Similar rules applies to the volumetric measurement available for the patients.

If a patient has more than one volumetric measurement available for a single target lesion in the time window associated with the index date (i.e., up to 24 weeks prior to the index date) or at 24 weeks (i.e., ± 4 weeks) following the index date, the measurement taken closest to the index date or 24 weeks following the index date will be considered in the analysis. If two volumetric measurements for a single target lesion were taken on dates that are equidistant from the index date or 24 weeks following the index date, the larger of the two measurements (i.e., greatest volume) will be considered. All measurements available will be listed.

Imputation rules for the dates are reported in the [Appendix](#).

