3.6 Secondary endpoints

Secondary endpoints will be used to support the efficacy of alpelisib, to provide a more complete description of the impact of alpelisib on the heterogeneous manifestations of PROS and to evaluate the safety and tolerability of alpelisib.

All the secondary endpoints including the safety analysis will be reported using the full population, to analyze data over time all available data will be used (Section 3.6.2). No imputation methods will be performed.

Endpoint #1: Percent change in the sum of target lesion (1 to 3 lesions) volume, as assessed by a central review of imaging scans, as measured by the change between the index date (or up to 24 weeks prior) and key time-points following the index date.

Endpoint #2: Percent change in sum of all measurable lesions (target and non-target) volume, as assessed by a central review of imaging scans, as measured by the change between the index date (or up to 24 weeks prior) and key time-points following the index date.

Endpoint #3: Percent change in the sum of all measurable non-target lesion volume, as assessed by a central review of imaging scans, as measured by the change between the index date (or up to 24 weeks prior) and key time-points following the index date.

In order to comprehensively demonstrate the efficacy of alpelisib treatment on target lesions, the percent change will be evaluated and reported at predefined time points throughout the study period (Section 3.3), under the assumption that a considerable number of patients have been treated for longer than 24 weeks.

Similarly as endpoint #1, the change in all measurable lesions, including the non-target, need to be assessed to confirm the potential benefit of alpelisib.

The percent change in the sum of measurable lesion volume (target and non-target) for each patient from index date to a generic key time point X (with X = 4, 12, 24, 36, 52 etc), will be calculated using the following equation:

$$\frac{\text{Sum}(\text{volume1}_{X\text{weeks}}, \text{volume2}_{X\text{weeks}}, \text{volume3}_{X\text{weeks}}) - \text{Sum}(\text{volume1}_{\text{index}}, \text{volume2}_{\text{index}}, \text{volume3}_{\text{index}})}{\text{Sum}(\text{volume1}_{\text{index}}, \text{volume2}_{\text{index}}, \text{volume3}_{\text{index}})} \times 100\%$$

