Growth and development will only be summarized for patients who were aged <18 years at the time of alpelisib initiation.

BMI (kg/m²) will be calculated as weight [kg] / (height² [m²]). Individual trajectories for height and BMI will be compared to growth standards from the World Health Organization. Data are available online at (<http://www.who.int/childgrowth/en/>). Height and BMI will be summarized through the standard deviation score (SD- score), velocity and velocity SDS.

Z-scores or SD- scores are used to describe how far a measurement is from the median (average). The distribution of heights of all boys (or all girls) of a certain age follows a normal (or almost normal) distribution. The z-score of an observed point in this distribution is calculated as follows: Z-score (or SD-score) = (observed value - median value of the reference population) / standard deviation value of reference population. These scores are calculated differently for measurements that are distributed normally and non-normally in the reference population (Interpreting growth indicator, WHO. https://www.who.int/childgrowth/training/module_c_interpreting_indicators.pdf?ua=1)

Height and BMI SDS will be summarized using descriptive statistics (mean, standard deviation, range), as well as by presenting number of patients with SDS values lower/higher than 5th/95th percentiles respectively. Shift tables will be provided to compare index date to the last available value recorded during study period. Box plots may also be plotted for each time window.

Height velocity is defined as follows:

$$\text{Height velocity (cm/6-months)} = (\text{height in time window } k - \text{height in time window } k-1) \\ \div ([\text{assessment date in time window } k - \text{assessment date in time window } k-1] \div [365.25/2]),$$

and similarly for weight velocity.

Velocity SDS is calculated as (velocity – mean) / SD, where mean and SD are obtained as the height-, weight-, sex- and age-specific values in Tables 5 to 8 in Baumgartner et al (1986), where the age category immediately above the patient's exact age (at the assessment date in time window *k*) should be used. Velocity SDS will only be calculated for time window *k* if data also exists for time window *k-1*, since calculating across multiple units of 6 months requires more than one reference value to be taken into account.

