4.1 General definitions

Study treatment

The term study treatment or study drug will be used in this document and will refer to alpelisib.

Date of first administration of study drug

The date of first administration of alpelisib is defined as the first date when a non-zero dose of alpelisib is administered and recorded in the (e)CRF. This date is referred to as index date and used as reference start date.

Date of last administration of study drug

The date of last administration of alpelisib is defined as is the last date when a nonzero dose of alpelisib is administered and recorded in the (e)CRF.

Study day

The study day, describes the day of the event or assessment date, relative to the reference start date. The study day is defined as:

- The date of the event (visit date, onset date of an event, assessment date etc.) – reference start date + 1 if event is on or after the reference start date;
- The date of the event (visit date, onset date of an event, assessment date etc.) – reference start date if event precedes the reference start date.

Time unit

A year length is defined as 365.25 days. A month length is 30.4375 days (365.25/12). If duration is reported in months, duration in days will be divided by 30.4375. If duration is reported in years, duration in days will be divided by 365.25.

Baseline

For safety and efficacy evaluations, the last available assessment on or before the date of start of alpelisib is defined as “baseline” assessment.

On-treatment assessment/event and observation periods

For adverse event reporting the overall observation period will be divided into two mutually exclusive segments:

1. *pre-index date/pre-treatment period*: from up to 24 weeks prior to the index date through to the day prior to the index date.
2. *post-index date/on-treatment period*: from date of first administration of study treatment to 30 days after date of last administration of alpelisib (including start and stop date).

Safety summaries (tables, figures) include only data from the on-treatment period with the exception of baseline data which will also be summarized where appropriate (e.g. change from baseline summaries).

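### Velocity SDS standardizes increments taken nominally 8 to 16 weeks apart with 6-month reference SDs, which widens its spread and overcounts children outside the 5th/95th percentiles

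*SAP*

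**What the plan says.** Under secondary objective #9, SAP 3.6 defines "Height velocity (cm/6-months") as the height difference between window k and window k-1, divided by the actual number of days between the two assessments expressed in half years (365.25/2 days). Weight velocity is defined in the same way.

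Velocity SDS is then (velocity − mean)/SD, where "mean and SD are obtained as the height-, weight-, sex- and age-specific values in Tables 5 to 8" of a cited set of incremental growth tables. "Velocity SDS will only be calculated for time window" k if window k-1 also has data, "since calculating across multiple units of 6 months requires more than one reference value to be taken into account". For each window the SAP reports mean, SD and range of velocity SDS, the number of patients below the 5th and above the 95th percentile, and box plots at key time points. The summary covers patients under 18 at the start of alpelisib.

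The windows come from SAP 3.3, Table 3-1. Their key time points are those also listed in SAP 3.6 ("with X = 4, 12, 24, 36, 52 etc"), and later ones follow this rule: "After week 52 intervals of approximately 11 weeks (e.g. 63 weeks, 74 weeks, etc.) with a time window of +/- 5 weeks". Where a window holds several values, "the measurement taken closest to the key-time point will be considered in the analysis".

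**The concern.** The reason given for the k-1 rule makes sense only if consecutive windows lie about one 6-month unit apart. In Table 3-1 no adjacent pair does so nominally. The SAP sets no minimum interval and does not adjust the reference SD for a shorter one.

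A short increment scaled up to 6 months carries its measurement error up with it, while the SD in the denominator describes a full 6-month increment. The SDS is then too widely spread, and both tails are overcounted.

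The k-1 rule also selects the wrong pairs. The increment from index to the 24-week window is close to the reference interval, but it is never used. If the 12-week window has data, the shorter gap is taken; if it is empty, no velocity SDS is calculated at 24 weeks.

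The study has no control arm, so the reference distribution is the only comparator for this table. If the scale is wrong, a count of children with unusually low or high growth velocity cannot be interpreted.

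**Working it through.** **Inputs from the documents**
- Half year: 365.25/2 = 182.625 days = 26.09 weeks. This agrees with SAP 4.1 ("A month length is 30.4375 days (365.25/12")), since 6 × 30.4375 = 182.625.
- Key time points (Table 3-1): 4, 12, 24, 36 and 52 weeks, then about every 11 weeks. Nominal gaps: 8, 12, 12, 16, then 11 weeks.
- Reference interval: 6 months, implied by the velocity unit and by the reason given for the k-1 rule.
- Nominal share outside the 5th/95th percentiles: 10%.

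The documents state no error rate for velocity SDS, so there is no figure of the plan to reproduce.

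**Assumptions, not in the documents**
- r = SD of one measurement divided by the 6-month reference SD, taken from 0.1 to 0.5.
- The reference SD already contains the error of the two measurements that form a 6-month increment.
- Each child's true velocity is constant over the interval, and the distributions are normal.

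**Formulas**
- Scale factor: c = 26.09/gap in weeks.
- Error variance of the scaled increment, in reference-SD units: 2r²c². The reference already includes 2r², so Var(SDS) = 1 + (c² − 1) × 2r².
- Share outside = 2 × [1 − Φ(1.645/√Var)]. At c = 1 this returns 10.0%.

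**Worked case**, 8 weeks and r = 0.3: c = 26.09/8 = 3.26 and c² = 10.635. Var = 1 + 9.635 × 0.18 = 2.734, so the SD is 1.654. Then 1.645/1.654 = 0.995, and the share outside is 32.0%. A simulation of this case gave 31.9%.

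**Share outside the 5th/95th percentiles (10% nominal)**

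| Gap (weeks) | c | r = 0.1 | r = 0.2 | r = 0.3 | r = 0.4 | r = 0.5 |
|---|---|---|---|---|---|---|
| 8 | 3.26 | 13.2% | 21.6% | 32.0% | 41.6% | 49.5% |
| 11 | 2.37 | 11.6% | 16.0% | 22.4% | 29.6% | 36.6% |
| 12 | 2.17 | 11.3% | 14.9% | 20.3% | 26.7% | 33.1% |
| 16 | 1.63 | 10.6% | 12.2% | 14.9% | 18.4% | 22.4% |
| 24 | 1.09 | 10.1% | 10.2% | 10.6% | 11.0% | 11.5% |

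For the share to double to 20%, r must be about 0.18 at 8 weeks, 0.30 at 12 weeks and 0.44 at 16 weeks.

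**Actual gaps.** The window limits allow adjacent measurements from days apart (either side of a boundary) up to just under 26 weeks (week 32 to just before week 58). The SAP does not say whether the index value counts as k-1 for the 4-week window. If it does, the nominal gap is 4 weeks, c = 6.52, and the share at r = 0.3 is 57%.

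**The case against.** Several points on the other side stand.

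- **The size rests on outside inputs.** If r is only 0.1, the excess is about 3 points at 8 weeks and under 1 point at 16. Only one nominal pair, 4 to 12 weeks, has the 8-week gap.
- **The mean is sound.** Velocity divides by actual elapsed days, so scaling does not bias mean SDS under steady growth. Mean and SD are both reported, so an inflated SD would be visible.
- **Other growth summaries are unaffected.** Height and BMI SDS, the shift tables from index to last value and the comparison with WHO growth standards use attained size and involve no scaling.
- **Adjacent windows can sometimes suit the reference.** A pair from the 36- and 52-week windows can approach 26 weeks, and choosing the value closest to the time point favours nominal spacing over very short gaps.

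A reader might infer three stronger things that the documents do not support.

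- **That measurement error alone puts many children outside.** The shares above include ordinary variation between children. Error with no true variation, at r = 0.3, gives 23.5%, 7.5% and 1.7% at 8, 12 and 16 weeks.
- **That the share could pass 60%.** Pairing a 0.5 cm error with a 0.7 cm reference SD gives about 62% at 8 weeks. But √2 × 0.5 = 0.707 exceeds 0.7, so true variance would be negative under the model used.
- **That growth is an identified safety risk of alpelisib.** Protocol section 3 says growth information was added to characterize clinical assessments better. It belongs to objective #9, and the list of adverse events of special interest has no growth item.

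None of this reconciles the 6-month rationale with the spacing in Table 3-1.

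**Conclusion.** The concern holds as an inconsistency in how one descriptive summary is built. The standardization presumes 6-month intervals, and the windows supply nominal intervals of 8 to 16 weeks. The direction follows from the formulas: with any non-zero measurement error, an interval shorter than 6 months gives velocity SDS a variance above 1 under the model used, and both tails are overcounted. The SD, range, box plots and percentile counts are affected.

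The size is conditional. For r from 0.1 to 0.5, with a reference SD that includes 6-month measurement error and steady growth, the share outside is 13-50% at 8 weeks, 11-33% at 12 weeks and 11-22% at 16 weeks, against 10%. The documents do not allow a narrower statement, and the figures do not extend to any particular error SD for weight.

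It should be corrected because the percentile counts have no other comparator and the correction is cheap.

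**What to change.** Replace the k-1 rule in SAP 3.6. Calculate velocity SDS only from pairs of measurements about 6 months apart, judged on actual dates, with both a minimum and a maximum gap (for example 20 to 32 weeks):
- baseline to the 24-week window;
- the 24-week to the 52-week window (nominally 28 weeks);
- after that, the window nearest 26 weeks later. On the 11-week grid this is two windows on, nominally 22 weeks.

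List pairs outside the range without standardizing them.

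The maximum is needed as well as the minimum. SAP 4.1 takes baseline as the last value on or before the start of alpelisib, and the pre-index period reaches back 24 weeks. A baseline to 24-week pair could therefore span almost 24 + 32 = 56 weeks, which would bring back the multiple-unit problem that the k-1 rule was meant to avoid.

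The text should also say how the end-of-study window is treated. SAP 3.3 lets one assessment fall both there and in a regular window, which would leave an interval of zero.

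On the same assumptions, the share outside is 10-12% at a 24-week gap and 10-13% at 22 weeks. At the 20-week minimum it is 10-16%. The cost is a change of SAP wording, a different pairing of values already abstracted, and fewer velocity SDS values per child. No new data are needed.

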Study design	
See Section 6.1 for additional information.
 
This study will be a site-based retrospective non-interventional medical chart review of pediatric and adult male and female patients with PROS who initiated alpelisib at least 24 weeks before the cut-off date at a MAP site. The study cut-off date is 09-Mar-2020.
 
Patient-level data will be abstracted from medical charts of all eligible patients at all participating sites. The pre-index (pre-baseline) period will be defined as the period from up to 24 weeks prior to the index date (baseline) through one day prior to the index date. The index date (baseline) is defined as the date of alpelisib initiation. The study period is the period from the index date up to the most recent data available at the time of the cut-off date (Figure 6-1).
 
Information from patients treated with alpelisib will be used to describe the efficacy and safety of alpelisib in patients with PROS.

Setting and study population	
See Section 6.2 for additional information.
 
Patients will be included in this study if they meet all of the following inclusion criteria:
 
 
• Patient (adult or pediatric) is <math>\geq 2</math> years of age*
 
• Patient has a physician confirmed/documented diagnosis of PROS*
 
• Patient has documented evidence of a mutation in the PIK3CA gene*
 
• Patient's condition was assessed by the treating physician as severe or life-threatening and treatment was deemed necessary*
 
• Patient has been treated with at least one dose of alpelisib, initiated on or before 23-Sep-2019 (ie: at least 24 weeks before the cut-off date of 09-Mar-2020)
 
• Patient has medical chart history available during enrollment in the MAP
 
• Patient (in case of pediatric patients assent and/or parent/guardian consent) consented to participate in the study (as required by local ethics regulations)
 
 
*Inclusion criteria for MAP enrollment (assessed at the time of alpelisib initiation).

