## **8 Management and reporting of adverse events/adverse reactions**

As this is a study based on secondary use of data, no individual safety reports will be made. Safety events and other safety-relevant results will be provided down to an individual level in datasets in the study report. Adverse events are collected from the index date through 30 days after the last dose of study treatment until the cut-off date. If a death occurs after the cut-off date but within 30 days after the last dose of alpelisib, this event should still be reported.

In studies based on secondary use of data with a safety-relevant result, reports of adverse events/adverse reactions will be summarized in the study report (i.e., only the overall association between an exposure and an outcome will be presented). Relevant findings from the study report can be included in the periodic aggregated regulatory reports submitted to Health Authorities by Novartis.

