Height/weight SDS and velocity SDS will be summarized using descriptive statistics (mean, standard deviation, range) for each time window, as well as by presenting number of patients with SDS values lower/higher than 5th/95th percentiles respectively. Box plots will also be plotted for key time points.

Endpoint #10: Type, frequency, seriousness, and severity criteria and causality assessments of treatment-emergent adverse events.

Adverse events summary tables will report only on-treatment assessments/events (more details in [Appendix](#)). An on-treatment adverse event is defined as any adverse event reported in the following time interval (including the lower and upper limits):

- date of first administration of study treatment; date of last administration of study treatment + 30 days or cut-off date whichever occurs first

The endpoint will report adverse events defined as the appearance of (or worsening of any pre-existing) undesirable sign(s), symptom(s), or medical condition(s) that occur during the study period. The full population will be used for reporting Adverse Events (AE) and all safety endpoints. As much as possible, each AE will be evaluated to determine:

- Toxicity grade
- Impact (“Low”, “Medium” and “High”)
- Duration
- Relationship to the study treatment (i.e., not related, related, unknown)
- Whether it is serious as per medical chart
- Action taken with respect to study treatment (i.e. dose increased; dose not changed; dose reduced; drug interrupted; drug withdrawn). If a concomitant medication or additional therapy was provided (for example diet for impaired glycemic control)
- Outcome (i.e., not recovered/not resolved, recovered/resolved, recovering/resolving, recovered/resolved with sequelae, fatal, unknown)

All AEs collected in the AE eCRF page will be listed along with the information collected on those AEs e.g. AE relationship to study drug, AE outcome etc.

AEs will be summarized by number and percentage of patients having at least one AE in each primary system organ class (SOC) and for each preferred term (PT) using MedDRA coding. A patient with multiple occurrences of an AE will be counted only once in the respective AE category. A patient with multiple CTCAE grades (version v4.03) for the same preferred term will be summarized under the maximum CTCAE grade recorded for the event. AE with missing CTCAE grade will be included in the ‘All grades’ column of the summary tables.

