day, month	
 If available year = year of study treatment start date (index date) then set start date = max(study treatment start date, 01JulYYYY). If available year > year of study treatment start date then 01JanYYYY If available year < year of study treatment start date then max (01JulYYYY , Pre-Index date)
Day	
 o If available month and year = month and year of study treatment start date then set start date = max(study treatment start date, 15MONYYYY). • If available month and year > month and year of study treatment start date then 01MONYYYY • If available month and year < month year of study treatment start date then max(15MONYYYY , Pre-index date)

If imputed date is before birth or after DCO, death date or study discontinuation the last will be used.

If imputed end date is earlier than the start date or of the imputed start date then the imputed end date = start date.

Any AEs and ConMeds with partial/missing dates will be displayed as such in the data listings.

Any AEs and ConMeds which are continuing as per data cut-off will be shown as 'ongoing' rather than the end date provided.

For treatment start and end date if day is missing then it will be set to be the 15th of the month and if both month and day are missing, is defaulted to 01-Jan.

Treatment end date = min (imputed treatment end date*, death date, cut-off date).

If Imputed treatment end date < Treatment start date then Treatment end date= treatment start date.

Similar imputation will be performed for similar assessment in the pre-index period, more details as will be provided in the PDS.

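### SAP 3.6 and SAP 4.1 disagree on whether the on-treatment period stops at the cut-off, and neither carries the protocol's exception for deaths after it

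*SAP*

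**What the plan says.** Protocol section 2 fixes the date: "The study cut-off date is 09-Mar-2020". Protocol section 8 sets the general rule: "Adverse events are collected from the index date through 30 days after the last dose of study treatment until the cut-off date". It then makes one exception: "If a death occurs after the cut-off date but within 30 days after the last dose of alpelisib, this event should still be reported".

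The SAP defines the on-treatment window twice.

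- SAP 3.6, under endpoint #10, restricts the tables: "Adverse events summary tables will report only on-treatment assessments/events". The interval starts at first dose and ends at "date of last administration of study treatment + 30 days or cut-off date whichever occurs first". The same sentence on the tables refers to the Appendix for details.
- SAP 4.1, in that Appendix, defines the on-treatment period as "from date of first administration of study treatment to 30 days after date of last administration of alpelisib". It sets no cut-off limit and adds: "Safety summaries (tables, figures) include only data from the on-treatment period", apart from baseline data.

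SAP 3.6 names an overview covering both adverse events and deaths among the adverse event summaries. It gives no separate window for the deaths. It also lists every adverse event collected on the eCRF page. SAP 1.3 ends the study period at the cut-off. The protocol's exception for deaths appears nowhere in the SAP.

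**The concern.** A programmer following 3.6 and one following 4.1 would use different windows for the same overview table. The difference bears on exactly the events for which the protocol makes an exception. A patient who dies shortly after 09-Mar-2020, on alpelisib or recently off it, is outside the first window and can be inside the second.

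Safety and tolerability is objective 10, and protocol section 9 intends the results for health authorities. The overview is also the main place where deaths would be counted. Protocol 6.8.2 plans adverse event outcomes, which include fatal, as numbers and percentages of patients. The list of summaries in SAP 3.6 has an outcome summary only for adverse events of special interest.

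The situation can arise in practice. The protocol amendment of 04-May-2020, 56 days after the cut-off, states that no patient had yet been enrolled. Deaths in the weeks after the cut-off could therefore already be known when charts were abstracted.

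**Working it through.** **Date check.** Protocol 6.2.1 gives 23-Sep-2019 as the latest start of alpelisib, at least 24 weeks before the cut-off. 23-Sep-2019 + 24 × 7 = 168 days gives 09-Mar-2020, so the plan's own figure is reproduced.

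**The two windows.** Inputs are the cut-off (Protocol section 2) and the two end rules (SAP 3.6 and 4.1).

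- SAP 3.6 end = min(last dose + 30 days, 09-Mar-2020)
- SAP 4.1 end = last dose + 30 days
- Days in dispute = SAP 4.1 end − SAP 3.6 end

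| Last dose | End under 3.6 | End under 4.1 | Days in dispute |
|---|---|---|---|
| 08-Feb-2020 | 09-Mar-2020 | 09-Mar-2020 | 0 |
| 09-Feb-2020 | 09-Mar-2020 | 10-Mar-2020 | 1 |
| 20-Feb-2020 | 09-Mar-2020 | 21-Mar-2020 | 12 |
| 01-Mar-2020 | 09-Mar-2020 | 31-Mar-2020 | 22 |
| 09-Mar-2020 | 09-Mar-2020 | 08-Apr-2020 | 30 |

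For last doses up to the cut-off, the sections differ only from 09-Feb-2020 onward, by 1 to 30 days.

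**Patients still treated at the cut-off.** For duration of exposure, SAP 3.6 sets their last exposure date to the cut-off. If the same date feeds the 4.1 window, that window ends on 08-Apr-2020. A patient who continued alpelisib and died in, say, June 2020 within 30 days of the last dose would meet the protocol's exception but fall outside both SAP windows. If the true later dose date is used, 4.1 includes that death. The end of the protocol's window for such patients depends on dosing after the cut-off and cannot be calculated from the documents.

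**Each rule against Protocol section 8.**

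| Event after the cut-off, within 30 days of last dose | Protocol section 8 | SAP 3.6 | SAP 4.1 |
|---|---|---|---|
| Non-fatal adverse event | not collected | outside | inside |
| Death | still reported | outside | inside, at least to 08-Apr-2020 |

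SAP 3.6 matches the protocol for non-fatal events but not for deaths. SAP 4.1 accommodates the deaths but drops the cut-off for everything else.

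**Scale, as illustration only.** Protocol Table 6-2 uses 50 patients. If one such death occurred among 50, the tabulated proportion would be 0/50 = 0% under one section and 1/50 = 2% under the other (Clopper-Pearson 95% CI 0.05% to 10.6%). Nothing in the documents shows that such a death occurred.

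**The case against.** The strongest reply has three parts.

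First, SAP 3.6 follows the protocol where adverse events are concerned, because section 8 itself stops their collection at the cut-off. This stands; only the sentence on deaths is at issue.

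Second, the 3.6 interval is written for adverse events, the deaths part of the overview has no stated window, and 3.6 refers to the Appendix, where 4.1 would include the deaths. This stands in part. It shows that exclusion is not certain. However, the overview is named among the adverse event summaries, which 3.6 restricts to its own interval, and no other rule for deaths is given. Nothing tells the programmer that 4.1 prevails.

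Third, the protocol asks that the death be reported, which need not mean tabulated. All adverse events on the eCRF page are listed, and section 8 promises individual-level data. A listing may well satisfy that sentence, so a breach of the protocol is not shown. It does not settle which deaths the overview counts.

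The endpoint is also secondary and descriptive, with no hypothesis test, and the primary endpoint is untouched. That limits the severity.

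**Conclusion.** The contradiction between SAP 3.6 and SAP 4.1 is on the page, and the protocol's exception for deaths is missing from both. Under 3.6, a death after 09-Mar-2020 and within 30 days of the last dose is left out of the overview. Under 4.1 it is in, at least up to 08-Apr-2020. The documents give no number of such deaths, no number of patients still treated at the cut-off and no mortality rate, so no expected count can be derived and the effect may be zero. Severity is minor to moderate.

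A reader might infer more, in three ways that the documents do not support.

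- *That these deaths disappear from the safety reporting.* They are excluded from the table only if 3.6 governs, and they can still appear in listings.
- *That the rule "Treatment end date = min (imputed treatment end date*, death date, cut-off date") closes the window at the cut-off.* It stands among the date-imputation rules of SAP 4.3.1. SAP 4.1 separately defines the last administration as the last recorded non-zero dose. Even with last exposure set to the cut-off, the 4.1 window reaches 08-Apr-2020.
- *That Amendment 2 made matters worse by moving fatal-outcome adverse events to listings.* That entry is version history, and the current SAP still plans an overview that includes deaths.

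**What to change.** 1. Use one on-treatment definition in SAP 3.6 and SAP 4.1. For non-fatal adverse events, end it at the earlier of last dose + 30 days and the cut-off, in line with Protocol section 8.
2. State in both sections that deaths after the cut-off but within 30 days of the last alpelisib dose are counted in the overview of deaths, flagged as post-cut-off, and listed.
3. Record the last-dose date for each such death. Section 8 requires the death to be reported, but no passage plainly requires dosing dates after the cut-off.

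The cost is a few lines of SAP text and one date for each affected patient. There is one drawback: exposure is truncated at the cut-off, so these deaths and the exposure summary cover slightly different periods. Showing the flagged deaths on a separate line, rather than merging them into the count up to the cut-off, keeps both figures interpretable.
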